6.1.5 Exit Visit

Do not continue with the Exit Visit until/unless the subject is ready to exit the study. Subjects who require further follow-up at the conclusion of the 3-Month Follow-up Visit will be followed according to the AE and/or Unscheduled Visit Section until the AE is resolved or stabilized.

The Exit Visit will proceed as follows:

- a. Indicate status of the subject on the Subject Exit Form. If the status is "Discontinued" or "Non-dispensed," indicate the PRIMARY exit reason for each eye on the Subject Exit Form.
- b. For all subjects, complete an exit ocular examination without lenses on the eyes. Collect the following assessments:

- Spherocylindrical refraction
- BSCVA Contrast Distance Lens VA
 - Compare the Exit Visit distance BSCVA to the distance BSCVA obtained at the Screening/Dispensing Visit. If the VA has decreased by 10 letters (0.2 logMAR) or more, explain.
- Keratometry
 - For each eye, compare the Exit visit Horizontal and Vertical keratometry readings to the Screening/Dispensing Visit Horizontal and Vertical keratometry readings. If there is a change of 1.00 D or more, explain.
- c. Indicate if there were any changes to pre-existing corneal scars.
- d. Unmasked designee to collect all worn lenses from the subject. All worn lenses will be returned to the Sponsor in lens cases filled with *Bausch + Lomb Sensitive Eyes*® *Saline Solution* at the end of the study. Place the lens case in a labeled zippered bag.
- e. Unmasked designee to collect used Study Kit (bottle and carton) dispensed at the subject's previous visit.

- f. Unmasked designee to place the lens case in the labeled zippered bag and the used Study Kit (bottle and carton) in the subject's bag. DO NOT seal subject bags until a full study accountability is performed by a Clinical Monitor at the end of the study.
- g. All study materials (refer to Section 4.4.2) must be returned to the Sponsor at the end of the study.
- h. Have the subject complete the Subject Assessment Questionnaire.

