3.3.3 Subject Discontinuation

A subject MAY be discontinued (at the discretion of the Investigator, the Sponsor, and/or the IRB) prior to the final study visit for a variety of reasons, including, but not limited to:

- An AE occurring during the course of the study, which precludes continued treatment or follow-up
- Persistent grade 3 or 4 slit-lamp findings
- Persistent study related symptoms/complaints
- Unacceptable distance lens visual acuity (VA)
- Unacceptable lens centration
- Unacceptable lens movement
- Failure to follow study procedures

A subject MUST be discontinued prior to the final study visit for any of the following reasons:

- Voluntary withdrawal
- Death
- Investigator decision that it is not in the best medical interest of the subject to continue participation in the investigation
- Lost to follow-up (refer to Section 3.3.4)
- Either eye is discontinued
- Becomes pregnant during the study

Prior to discontinuing a subject, every effort should be made to contact the subject, schedule a final study visit, obtain as much follow-up data as possible, and to retrieve all study materials. Adverse events will be followed as described in Section 7.0.

Subject discontinuations must be documented clearly on the source document and applicable eCRF. The Investigator should indicate the PRIMARY (one) reason that the subject was discontinued for each eye. Subjects who voluntarily withdraw from the study are not required to provide a reason for their decision but should be encouraged to share

this information. Subjects that are discontinued from the study following randomization will not be replaced.

Exit Visit assessments should be completed for early discontinued subjects, if possible.

At the final study visit, all study subjects who are discontinuing should be examined to ensure that their ocular health is consistent with pre-study, baseline conditions. Any adverse effects determined to have been reasonably caused by participation in the study will be followed per the standard of care. Participation in the study will not impact poststudy choices of study subjects for correcting their vision using marketed products (e.g., contact lenses and contact lens care solutions).

Whether a subject completes or is discontinued from the study, they will be directed by the Investigator to resume their habitual lens care regimen.

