8.1.4 Primary Safety Endpoint

The primary safety endpoint is the proportion of eyes with any slit-lamp findings greater than Grade 2 over all follow-up visits.

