APPENDIX A: SCHEDULE OF VISITS AND PARAMETERS

All study tasks should be performed by qualified study site personnel as indicated on the delegation of authority log under the supervision of the Principal Investigator. (Refer to important footnotes at the bottom of the table)

PROCEDURES / ASSESSMENTS	Screening/ Dispensing	2-Week Follow- up Visit	1-Month Follow- up Visit	2-Month Follow- up Visit	3-Month Follow- up Visit	Exit Visit °	Unscheduled Visit ^g
	Day 1	Day 11-19	Day 27-35	Day 54-68	Day 84-98		
Informed Consent / HIPAA Authorization	Х						
Eligibility	Х						
Demographics/ Medical History	X						
Concomitant Medications	X	Х	Х	Х	Х	Х	X
Adverse Events; Cultures Taken if Appropriate ^d	X	Х	Х	Х	Х		X
Baseline Lens / Lens Care History	X						
Lens Wear Parameters	X	Х	Х	Х	Х		X
Habitual Lens Symptoms/Complaints ^b	х						
Symptoms/ Complaints Form ^b (Study Lenses Symptoms/Complaints)		X	х	Х	Х		Х
Exit Form (if an Exit Visit took place)	X a	X	Х	Х	Х	Х	X
Subject Completed Forms							
(Habitual Lens) Lens Performance Assessment ^b	X						
Abbreviated Lens Performance Assessment Form ^b (Study Lenses Performance Rating Scales)	х						
Study Lens Performance Assessment Form ^b (Study Lenses Performance Rating Scales)		X	Х	Х	Х		х
Subject Assessment Questionnaire						Х	
Without Lenses	-			-			
Spherocylindrical Refraction ^c	Х					Х	

PROCEDURES / ASSESSMENTS	Screening/ Dispensing Day 1	2-Week Follow- up Visit Day 11-19	1-Month Follow- up Visit Day 27-35	2-Month Follow- up Visit Day 54-68	3-Month Follow- up Visit Day 84-98	Exit Visit °	Unscheduled Visit ^g	
Distance BSCVA ^c	X					Х		
Keratometry	Х					Х		
Slit-lamp Examination	Х	Х	Х	Х	Х		Х	
Compare Distance BSCVA to Screening / Dispensing Visit Distance BSCVA ^c						X e		
Compare Final Keratometry to Screening / Dispensing Visit Keratometry ^c						Х		
With Lenses Worn to Visit								
Distance Lens VA ^c		Х	Х	Х	Х		Х	
Over-Refraction and Distance VA ^c		Х	Х	Х	Х		Х	
Lens Wettability		Х	Х	Х	Х		Х	
Lens Deposits (type, percent, and degree)		Х	Х	Х	Х		X	
Lens Centration		Х	Х	Х	Х		X	
Lens Movement		Х	Х	Х	Х		X	
Compare Distance Lens VA to Distance Lens VA at Screening / Dispensing Visit ^c		X	X	Х	Х		х	
With Newly Dispensed Lenses			-					
Distance lens VA ^c	Х		Х	Х			Х	
Over-Refraction and Distance Lens VA ^c	Х		Х	Х			Х	
Lens Wettability	Х		Х	Х			X	
Lens Centration	Х		Х	Х			X	
Lens Movement	Х		Х	Х			X	
Compare Distance Lens VA to Distance Lens VA at Screening/ Dispensing Visit ^c			Х	Х			Х	

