PROCEDURES / ASSESSMENTS	Screening/ Dispensing	2-Week Follow- up Visit	1-Month Follow- up Visit	2-Month Follow- up Visit	3-Month Follow- up Visit	Exit Visit °	Unscheduled Visit ^g	
	Day 1	Day 11-19	Day 27-35	Day 54-68	Day 84-98			
Compare Distance Lens VA to Distance BSCVA at Screening/ Dispensing Visit ^c	х							
Study Materials								
Dispense Lenses	Х		Х	Х			Х	
Randomization	Х							
Dispense Study kit ^h	Х		Х	Х			Х	
Dispense other Supplies as Needed (Refer to Protocol Section 4.4.3)	Х	Х	Х	Х			Х	
Collect Worn Lenses from Subject ^h			Х	Х	Х	Х	Х	
Collect Study Kit ^h			Х	Х	Х	Х	Х	
Return Study Materials to Sponsor at End of Study ^f						Х		

a = At the Screening Visit, only complete the Exit Record for study participants who were randomized

b = Use rating scales provided

c = All VA measurements MUST be made using a phoropter

d = Reporting s begins when the informed consent form is signed by the study subject.

e = At any visit, if a randomized patient is exiting from study, perform the procedures listed in the Exit Visit column. In the presence of some adverse events, premature withdrawals and other rare situations, some Exit Visit procedures may be omitted. Document the reason for all omissions.

f = Sites need to keep all study materials until a full accountability is performed by study clinical monitor.

g = Perform assessments according to the Investigator's judgement

h = Unmasked designee

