#### **4.1.4. Definition of Study Time Points**

Visits will consist of the screening/dispensing visit, several follow-up visits, and the Exit visit. There is also the possibility for unscheduled visits. The following definitions will be used for classifying visits:

- Baseline (Day 1) will be defined as the screening/dispensing visit.
- Scheduled follow-up visits will include any of the following visits:
  - 2-Week Follow-up Visit
  - 1-Month Follow-up Visit

- 2-Month Follow-up Visit
- 3-Month Follow-up Visit

Any unscheduled visit (which may include the exit visit) which occurs after baseline will be considered a follow-up visit (but not a scheduled follow-up visit) for all analyses. For example, if a slit-lamp finding greater than Grade 2 occurs during an unscheduled visit after baseline, it will be included in the analyses for the primary safety endpoint.

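### The Exit Visit lists no slit-lamp examination and the rules for unscheduled visits conflict, so a subject who exits between scheduled visits can leave without the examination that defines the primary safety endpoint

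*Protocol*

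**What the plan says.** **Endpoint.** Protocol 8.1.4: "The primary safety endpoint is the proportion of eyes with any slit-lamp findings greater than Grade 2 over all follow-up visits". SAP 4.5.1 specifies scheduled and unscheduled follow-up visits and classifies each eye from its non-missing observations. SAP 4.1.4 adds: "Any unscheduled visit (which may include the exit visit) which occurs after baseline will be considered a follow-up visit".

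**Exit Visit.** Protocol 6.1.5 step b: "For all subjects, complete an exit ocular examination without lenses on the eyes. Collect the following assessments". The list is refraction, spectacle-corrected acuity and keratometry. Step c asks about changes to existing corneal scars, and step h is the questionnaire. In Appendix A the row "Slit-lamp Examination" is marked at Screening, at the four scheduled follow-up visits and at Unscheduled, but not at Exit. Footnote e reads "At any visit, if a randomized patient is exiting from study, perform the procedures listed in the Exit Visit column".

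**Unscheduled visits.** Section 6.1.6 step i lists a slit-lamp examination with no condition attached. But the section's lead-in makes procedures depend on the reason for the visit, step b leaves assessments to the Investigator when the subject has problems, and Appendix A footnote g says of the whole column "Perform assessments according to the Investigator's judgement". Step o sends a subject who exits at such a visit to 6.1.5.

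**Discontinuation.** Protocol 3.3.3 says discontinuing subjects "should be examined to ensure that their ocular health is consistent with pre-study, baseline conditions", and asks for the Exit Visit assessments in early leavers if possible.

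**The concern.** The visit at which a subject leaves is the last chance to grade the cornea and conjunctiva for the primary safety endpoint. It is also the visit at which 3.3.3 wants ocular health checked against baseline. Baseline ocular health was established largely by slit-lamp (exclusion criteria 13 to 16), so refraction, acuity and keratometry cannot confirm a return to it.

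The reasons for discontinuation in 3.3.3 include adverse events and persistent symptoms, so early leavers may well carry more findings than average. An eye with a clean 2-week examination and an unseen Grade 3 finding at a later exit is classed as Absent. An eye with no follow-up slit-lamp examination contributes nothing. Events missed in both arms shrink the Test minus Control difference, which in a non-inferiority comparison moves the result towards success.

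**Working it through.** **1. Who is affected.**

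| Route out of the study | Slit-lamp required? |
|---|---|
| Completes at 3 months | Yes: 6.1.4 step f |
| Exits at the 2-week, 1-month or 2-month visit | Yes: that visit's own steps (6.1.2 step f, 6.1.3 step g) |
| Exits at an unscheduled visit | Conflict: 6.1.6 step i and the Appendix A mark say yes; step b and footnote g leave it to judgement |
| Attends only an Exit Visit | Not listed: 6.1.5 step b, Appendix A Exit column |
| Lost to follow-up | No visit takes place |

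The gap is confined to the third and fourth rows. (A cross-reference in 6.1.4 step e that skips step f is a separate matter and is not counted here.)

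**2. The plan's own figure.** Inputs from Protocol 8.3.4: 300 eyes per arm, 0.8% in both arms, margin 5%, Newcombe-Wilson upper 97.5% limit, eyes independent. With Wilson limits l and u for each arm, the upper limit is

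U = (pT − pC) + √[(uT − pT)² + (pC − lC)²].

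Summing the two binomial probabilities over all pairs of counts with U < 5% gives power 99.94%, which agrees with the stated 99%.

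**3. How close the decision is.** Two Control eyes with events is near the expected 300 × 0.008 = 2.4. For 2/300, pC = 0.00667 and lC = 0.00183.

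- Test 9/300: pT = 0.0300, uT = 0.05602. U = 0.02333 + √(0.02602² + 0.00484²) = 4.98%, pass.
- Test 10/300: pT = 0.03333, uT = 0.06026. U = 0.02667 + √(0.02693² + 0.00484²) = 5.40%, fail.

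Near the boundary one eye decides.

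**4. How many eyes could be missed.** Planned losses are up to 10% of 340 subjects (Protocol 8.3.7): 34 subjects, 17 per arm, 34 of 340 eyes per arm. This is a ceiling. It includes subjects lost to follow-up and subjects who exit at a scheduled visit.

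**5. Effect at the margin.** Take Control 0.8% and Test 0.8% + 5% = 5.8%, with 340 eyes per arm. Expected Test events: 340 × 0.058 = 19.7.

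- Full ascertainment: probability of passing 2.3%.
- Leavers have the same event rate, every one of their events goes unseen, and their eyes stay in the denominator as Absent: 34 × 0.058 = 2.0 Test events missed, or 10%. The observed rates become 5.22% and 0.72%, and the probability of passing is 5.0%.
- Half of those events missed (5%): 3.4%.
- Leavers have no follow-up slit-lamp at all and drop out, at the same event rate: 340 − 34 = 306 eyes per arm, rates unchanged, probability of passing 2.0%. In this case bias needs a higher event rate among leavers.

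**6. What larger losses would require.** Missing 20% of Test events means 0.20 × 19.7 = 3.9 events in 34 eyes, a rate of 11.6%. Missing 30% means 5.9 events, a rate of 17.4%. Both require that no such eye is examined.

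**The case against.** **The unscheduled visit already has the examination.** Step i of 6.1.6 carries no condition, step h sends a subject without lenses straight to it, the Unscheduled column is marked, and the exit instruction (step o) comes after it. A reader might infer from footnote g that the slit-lamp is simply optional at unscheduled visits. The documents do not support that. They conflict, and the conflict is the defect. It remains a defect, because a site can follow step b or footnote g and omit the examination.

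**Footnote e adds to a visit rather than replacing it.** Its opening words fit a reading in which the Exit column is performed on top of that visit's own procedures. That is the more natural reading when a scheduled visit is under way. It does not help when the visit is held only for exit, since 6.1.5 then supplies the whole list.

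**Some important leavers are covered.** Persistent Grade 3 or 4 findings are a listed reason for discontinuation, and those events have already been recorded. Staining of Grade 3 or more and symptomatic infiltrative events need expedited reporting and follow-up. This holds, and lowers the likely number missed. It does not cover a finding that nobody looked for at exit.

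**Missing data are stress-tested.** SAP 4.5.3 applies best- and worst-case imputation and a tipping-point analysis to slit-lamp findings, and SAP 4.10 records the safety tipping point as an addition. An early leaver misses later scheduled visits, so the worst case can set Test eyes to Present. This is a real safeguard against the bias. But these are sensitivity analyses in the ITT Population, while the primary decision uses observed data in the Safety Population.

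**Conclusion.** The gap stands, with a modest expected effect. The Exit Visit omits the slit-lamp examination in both the text and the schedule. The unscheduled-visit rules contradict each other. Section 3.3.3 asks for a comparison with baseline that the listed exit tests cannot make.

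With equal event rates in leavers and none examined, at most about 10% of events are missed, and the probability of passing at the margin goes from about 2.3% to about 5.0%. This assumes independent eyes, as the plan does, 340 eyes per arm, and unseen eyes classed as Absent. If both arms truly sit at 0.8%, power is 99.94% at the planned 300 eyes per arm and a reversal is unlikely. The point matters when Test is worse, which is the case a safety test exists to detect.

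Two stronger readings should be avoided. A reader might infer an error rate of 10% to 18% from assumed losses of 20% or 30% of events. The documents give no rate of exits without a slit-lamp examination, and such losses need event rates among leavers of two to three times the 5.8% assumed, with none examined. A reader might also take SAP 4.1.4 as saying that every exit visit counts towards the endpoint. It says only that unscheduled follow-up visits may include it.

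**What to change.** 1. Add the graded slit-lamp examination (Appendix B, Section 2.0) to Protocol 6.1.5 step b and mark it in the Exit Visit column of Appendix A, unless one was done at the same visit.
2. Reconcile 6.1.6 step b and Appendix A footnote g with 6.1.6 step i, so that the slit-lamp examination is done whenever a subject exits at an unscheduled visit.
3. Confirm in SAP 4.5.1 that exit-visit grades fall under its scheduled and unscheduled follow-up visits. No new analysis rule is needed.

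The cost is protocol and eCRF wording, plus a few minutes of a routine examination for early leavers at a visit already held. Sample size and planned power do not change. A few more events may be counted, which could make the safety result slightly less favourable. The change cannot recover subjects who attend no exit visit; for them the sensitivity analyses in SAP 4.5.3 remain the safeguard.

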 - Average hours of comfortable wear (since last visit)
 - Hours lenses worn on the day of this visit
 - Did subject replace their lenses? (If so, when)
 - Last date that lenses were worn after cleaning and storing them in study solution
 - Number of days on study that the subject did not wear the study lenses
 - Percentage of days on study that the subject used study solution and wore their lenses on average (less than 80% = fewer than four out of five days, or 80% or more = at least four out of five days)
- b. Complete the Symptoms/Complaints Form (Study Lenses Symptoms/Complaints Rating Scales).
- c. Have the subject complete Lens Performance Assessment Form (Study Lenses Performance Rating Scales), including use of rewetting drops.
- d. Collect any relevant medical treatment information, including any adverse events, including whether a culture may have been taken.
- e. If the subject did not come to the visit wearing one or more study lenses, go to Step g. Otherwise, evaluate the lenses (while on eye):

- High contrast distance lens VA
- For each eye, compare the distance lens VA obtained at the Screening / Dispensing visit with the distance lens VA obtained at this visit. If the VA has decreased by 10 letters (0.2 logMAR) or more, provide an explanation.
- Over-refraction and distance VA
- Lens wettability
- Lens deposits (type, percent, and degree)
- Lens centration
- Lens movement
- f. Perform a slit-lamp examination (remove the lenses if the subject wore lenses to the visit). Record and sketch any scars and slit-lamp findings greater than Grade 2 in the subject's source document. If a corneal infiltrate is noted record details according to Corneal Infiltrates, Section 2.0: Slit-Lamp Examination of Appendix B: Methods of Clinical Evaluation.
- g. Unmasked designee to collect all worn dispensed lenses from the subject. All worn lenses will be returned to the Sponsor in lens cases filled with *Bausch + Lomb Sensitive*

Eyes ® *Saline Solution* at the end of the study. Place the lens case in a labeled zippered bag.

- h. Unmasked designee to collect used Study Kit (carton and bottle) dispensed at the subject's previous visit.
- i. Unmasked Designee to place the lens case in the labeled zippered bag and the used Study Kit (bottle and carton) in the subject's bag. DO NOT seal the subject's bags until a full accountability is performed by a Clinical Monitor at the end of the study.

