6.0 Subject Assessment Questionnaire

For completion of the Subject Assessment Questionnaire (conducted at Exit Visit), the Investigator or designee will instruct the subject to complete the form according to the care system care system that they have been using during the study. For each statement, the subject will check the box next to the appropriate number from 1 to 6, with 1 = strongly disagree and 6 = strongly agree. Boxes one through three will also be visibly grouped into a category named "disagree," while boxes four through six will be labeled as "agree." The statements are as follows:

- My lenses feel clean upon insertion
- Makes my lenses feel clean throughout the day
- Makes my lenses feel comfortable upon insertion
- Makes my lenses feel comfortable throughout the day
- Helps prevent dryness and discomfort
- My vision remains clear throughout the day
- Feels as gentle as natural tears
- Makes my lenses feel moist throughout the day
- Makes my lenses feel like a fresh pair
- Keeps my eyes feeling healthy
- Gives me a feeling of freedom to wear my lenses worry-free
- Provides long lasting comfort

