##### 4.7.2. Analytical Approach

For each statement, the proportion of subjects who “Agree” with the statement will be determined for Test and Control. Statistical testing will proceed in two hierarchical families of twelve statistical tests each (one test per statement), with the null hypotheses of the first family eligible for rejection if all the primary endpoints are met.

- The first family will employ a one-sided exact binomial test to compare the proportion of respondents in the Test group agreeing with each statement to 0.5.
- The second family will employ a one-sided chi-square test to compare the proportion of respondents agreeing with each statement between the treatment groups.

Within each family of hypothesis tests, the  $P$ -values will be adjusted for multiplicity using the Holm method; specifically, the raw (i.e. unadjusted) one-sided  $P$ -values will be adjusted using SAS PROC MULTTEST with the Holm option. Adjusted one-sided  $P$ -values less than 0.025 will show statistical significance. The second family will only be analyzed for significance if the entirety of the first family is statistically significant. This gatekeeping strategy will preserve the overall type I error rate of 0.025 across both families.

The responses to each statement will be summarized categorically by treatment group in a table for the ITT Set. The adjusted  $P$ -values from the statistical tests will also be displayed along with an indicator of statistical significance. If the statistical tests in a family are not eligible for rejection due to hierarchy, then the adjusted  $P$ -values for that family will not be displayed.

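### The Subject Assessment Questionnaire is completed after the exit examination, and its first family of tests, against a fixed 50%, would not cancel any influence of that order on the answers

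*Protocol*

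**What the plan says.** Protocol 6.1.5 introduces its steps with "The Exit Visit will proceed as follows" and letters them a to h. Step b is "For all subjects, complete an exit ocular examination without lenses on the eyes": refraction, best spectacle-corrected acuity and keratometry, with acuity and keratometry compared with the screening values. Step c is the scar check. Steps d to f collect lenses and kit, beginning with "Unmasked designee to collect all worn lenses from the subject". Step h, the last, is "Have the subject complete the Subject Assessment Questionnaire".

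Under Protocol 3.3.2 a subject completes the study by finishing the Exit procedures at the 3-Month visit. For these subjects the steps of 6.1.4 come first, including the on-eye lens evaluation (step e) and the slit lamp (step f: "Perform a slit-lamp examination (remove the lenses if the subject wore lenses to the visit"). Appendix B 2.0 requires fluorescein for corneal staining.

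The other subject-rated form at the 3-Month visit comes before both of these, at 6.1.4 step c: "Have the subject complete Lens Performance Assessment Form (Study Lenses Performance Rating Scales), including use of rewetting drops". The 2-Week, 1-Month and 2-Month visits use the same order.

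Appendix B 6.0 says of the questionnaire that "the Investigator or designee will instruct the subject to complete the form". SAP 4.7.2 analyses it in two families of twelve tests. The first uses a "one-sided exact binomial test to compare the proportion of respondents in the Test group agreeing with each statement to 0.5". The second compares the arms, and is tested only if all twelve statements in the first family are significant.

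**The concern.** Some of the twelve statements concern how healthy the eyes feel and whether vision stays clear through the day. A subject who has just read an acuity chart, and in most cases had a slit-lamp examination, may answer partly from that experience rather than from three months of using the solution.

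In a comparison of two masked, randomised arms, an influence shared by both arms largely cancels. Against a constant of 0.5 it does not: it moves the Test-group proportion, and the reference stays where it is. An upward influence would make agreement claims too easy to obtain. A downward one would cost power and, because the first family gates the second, could also block the better protected between-arm comparison. Holm adjustment and gatekeeping control multiplicity but do nothing about a shift in the recorded answers.

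**Working it through.** The documents give no expected agreement rate, sample size or power for the questionnaire, so there is no stated figure to reproduce.

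**Order of steps**

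| Visit | Subject-rated form | Examination |
|---|---|---|
| Screening/Dispensing (6.1.1) | step f (habitual lenses) | steps d–e, before the form |
| 2-Week (6.1.2) | step c | steps e–f, after the form |
| 1-Month and 2-Month (6.1.3) | step d | steps f–g, after the form |
| 3-Month (6.1.4) | step c | steps e–f, after the form |
| Exit (6.1.5) | step h (questionnaire) | step b, before the form |

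Among the scheduled post-treatment subject reports, only the questionnaire follows the examination.

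**Inputs for the illustration**
- Test respondents: n = 150, the planned Test-group completers (Protocol 8.3.7, SAP 2.2.6).
- Reference proportion 0.5, one-sided exact binomial, alpha 0.025, Holm over twelve statements (SAP 4.7.2).
- True agreement 50%, the boundary of the null hypothesis.
- Shift in recorded agreement: +3, +5 or +8 points. These are assumptions; the documents give none.

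**Critical counts.** Find the smallest r with P(X ≥ r) below the threshold, where X ~ Binomial(150, 0.5).
- Last Holm step, threshold 0.025: r = 88 (88/150 = 58.7%), exact size 0.0204.
- First Holm step, threshold 0.025/12 = 0.00208: r = 93 (93/150 = 62.0%), exact size 0.0021.

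Under Holm a statement always passes if its raw p-value clears the first-step threshold, and never passes if it misses the last-step threshold. Its chance of passing therefore lies between the two columns below.

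**Chance that a statement passes**, P(X ≥ r) with X ~ Binomial(150, p):

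| Recorded agreement p | First step (r = 93) | Last step (r = 88) |
|---|---|---|
| 0.50 (no shift) | 0.2% | 2.0% |
| 0.53 (+3) | 1.6% | 9.5% |
| 0.55 (+5) | 5.0% | 21% |
| 0.58 (+8) | 18% | 47% |

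**Downward shift.** If true agreement were 65% (also assumed) and recorded agreement 60%, the chance of passing would fall from 96% to 66% at the last step and from 80% to 34% at the first.

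**Second family.** With 150 per arm and the same shift in both arms, the one-sided chi-square test, by full enumeration, keeps a size of about 0.025 to 0.028 for common agreement between 50% and 80%. A shared shift does not inflate that comparison.

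**The case against.** The case against has real weight.

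- **The mechanism is not documented.** A reader might infer that subjects hear their results and are then coached by the examiner. The documents do not support this. No section says that findings are disclosed, and the form is introduced by the Investigator or a designee, who need not have examined the eyes. Protocol 9.3 bars staff from entering or changing data on subject-completed forms. The statements ask about the care system used during the study, so they call for recall over months. What stands is only that nothing prevents discussion of findings, and that the order allows an influence.
- **The slit lamp is not an Exit step.** The Exit examination is refraction, acuity and keratometry. The slit lamp belongs to the 3-Month or Unscheduled Visit and precedes the questionnaire on the same day only when exit takes place then.
- **The protocol has no universal form-first rule.** At Screening/Dispensing the examination also precedes the subject's rating form. The contrast holds for the scheduled follow-up visits only.
- **The shifts are invented, and the last Holm step is the most lenient.** That is why both steps are shown. With high agreement, the power loss would be small: a fall from 75% to 70% leaves 98.6% at the first step.
- **Moving the form is not wholly trivial.** Exit may be decided only after examination. Section 6.1.4 defers the Exit Visit when an adverse event is ongoing at 3 months, and Unscheduled Visits reach the exit decision at step o, after the slit lamp.

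The first four points limit the size and certainty of the concern without removing it. The last shapes the fix.

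**Conclusion.** The point holds as an avoidable exposure to response bias in a supportive outcome. The order of steps and the fixed 0.5 reference are plain in the documents, and a common shift would not cancel in the first family. Whether any shift exists, and in which direction, cannot be known from the documents, so it would be wrong to conclude that the agreement results are biased.

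The illustrated rise at +5 points, from 0.2% to 5.0% at the first Holm step and from 2.0% to 21% at the last, rests on n = 150, true agreement of 50% and an assumed shift. The four primary endpoints, the sample size and the safety conclusion are untouched, and the questionnaire is tested only if all four primary endpoints succeed. The between-arm family is largely protected by randomisation and masking, apart from its dependence on the first family as gate. This is a cheap improvement, not a flaw that threatens the trial.

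**What to change.** 1. In Protocol 6.1.4, have the questionnaire completed at the start of the 3-Month visit, together with the form in step c. Amend 6.1.5 step h and the Appendix A row to match.
2. For subjects exiting at any other visit, have it completed before the exit examination, and before lens evaluation and slit lamp where exit is already expected.
3. Add that findings are not discussed with the subject until the form is done.
4. State in SAP 4.7.1 that one questionnaire per subject is analysed: for example, the one from the 3-Month visit if completed, otherwise the one from the exit visit. Subjects kept on for an ongoing adverse event then do not supply two.

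The cost is a reordered step and one analysis rule, with no new procedure and no change to sample size or alpha. The downside is that a few forms may be collected from subjects who do not exit that day. The change does not remove other influences that a fixed benchmark cannot cancel.
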